2.1 Research aims

- In women with obesity (BMI≥30), what is the effect of in-person exercise coaching (high vs. medium vs. low dosage) on exercise adherence and total physical activity level?
- 2. In women with obesity (BMI≥30), what is the effect of in-person exercise coaching (high vs. medium vs. low dosage) on mental health variables (quality of life, self-efficacy and barriers and motivation to exercise)?

- 3. In women with obesity (BMI≥30), what is the effect of in-person exercise coaching (high vs. medium vs. low dosage) on health (glycated hemoglobin, cholesterol, blood pressure, waist circumference, BMI and urinary incontinence) and physical fitness (aerobic endurance, muscular strength)?
- 4. Is adherence to exercise and succeeding health effects associated with the exercise professionals' level of education and knowledge base?
- 5. What are the participant's experiences, barriers and facilitators of participating in the ABEL-project?
- 6. What are the general practitioners' experiences, barriers and facilitators of using the "green prescription"?

3. Method

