Muscular strength: Will be assessed by a 1-RM estimation test in: chest press, close • grip lat pull down and leg press. All exercises will be performed on the weight machines available at the specific location, and may therefore be slightly different. However, each participant will be tested on the same machine at baseline and followup. Two to three days before the 1-RM estimation test (test day), participants will undergo a familiarization session using each of the exercise equipment, according to the recommendations by Balady et al. (2000) (57). A load the participant perceives as low intensity will be selected for practice of correct lifting and breathing techniques (57). Practice continues until the participant demonstrates proper technique using submaximal loads, in all exercises for 10 repetitions. Participants will be asked to complete 10 repetitions for warm-up, using the load performed at the familiarization session. Thereafter, the load will progressively be increase until the participant reaches nine or less repetitions. Resting periods between attempts will be two minutes with a maximum of six attempts, and three minutes between each specific exercise. Brzycki 1-RM prediction equation (58) will be used to estimate the 1-RM based on the resistance and repetitions performed. The equation is mathematically expressed as 1RM = W/[102.78 - 2.78(R)]/100, where W is the weight used and R is the maximal number of repetitions performed.

In-depth interview:

• Women with obesity (n=15): In parallel with the RCT, 15 participants from the intervention groups (HIGH n = 5, MEDIUM n = 5, LOW dosage n = 5) will be recruited to participate in a semi-structured in-depth interview (approximately 60 min). The interview will be led by researchers from the project group, audiotaped and transcribed verbatim. An interview guide with open-ended questions will be developed by the project group, and based on: 1) Basic Psychological Needs in Exercise Scale (BPNES) (59, 60), that assess the extent to which the psychological needs of the participants were fulfilled during the intervention. BPNES includes three subscales, with four statements per subscale, to assess autonomy, competence, and relatedness. 2) A former investigation in Norway, including 14 questions designed to address factors associated with exercise adherence and drop-out (61). With regards to

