3.4 Data analysis

All statistical analysis will be performed using SPSS Statistical Software (IBM Corp. Released 2016. IBM SPSS Statistics for Windows, Version 24.0. Armonk, NY: IBM Corp). Difference in outcome measures between the groups will mainly be evaluated using analysis of variance (ANOVA), multivariate analysis of variance (MANOVA) and analysis of covariance (ANCOVA) The association between the exercise professional's level of education and knowledge base and participants adherence to exercise and/or improvement in health and physical fitness, will be assessed using linear regression, controlling for cofounding variables. Data will be presented as frequency, percentage or mean with standard deviation (SD). Transcripts from the in-dept interviews, will be analyzed using thematic analysis.

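### Does the 1-RM equation, printed without an outer bracket around its denominator, put the strength results at risk?

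*Protocol*

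**What the plan says.** Section 3.3 (Muscular strength) describes a 1-RM estimation test in chest press, lat pull-down and leg press. The load is raised until the participant manages nine repetitions or fewer. A named equation then converts load and repetitions into an estimate: the "prediction equation (58) will be used to estimate the 1-RM based on the resistance and repetitions performed". The protocol prints it as "1RM = W/[102.78 - 2.78(R)]/100, where W is the weight used and R is the maximal number of repetitions performed". It gives no worked value, and the equation does not appear anywhere else in the document.

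Strength enters the analysis in two places. Aim 3 in section 2.1 lists it under "physical fitness (aerobic endurance, muscular strength"). Section 3.4 plans ANOVA, MANOVA and ANCOVA for group differences, and a regression on the exercise professional's education and knowledge in which "improvement in health and physical fitness, will be assessed using linear regression, controlling for cofounding variables". On reporting, section 3.4 says: "Data will be presented as frequency, percentage or mean with standard deviation (SD").

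**The concern.** As typed, the line has two divisions at the same level. Read from left to right it means (W/[102.78 − 2.78R])/100. This fails the one check that needs no outside source: at R = 1 the estimate must equal the weight lifted.

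This is the only statement of the scoring rule for three outcome variables. If someone coded it literally, every strength mean, SD and between-group difference would be on the wrong scale. The unstandardized regression coefficients would be too, if improvement in strength is analyzed in absolute units. Section 4.2 says that master's students will have access to some of the data, so more than one person might apply the formula.

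**Working it through.** **Inputs.** The constants 102.78 and 2.78, the divisor 100, and the definitions of W and R come from section 3.3, as does the range R = 1 to 9. The loads below are assumed for illustration, in kilograms. The protocol reports no figure to reproduce, so the benchmark is the definition of a 1-RM: R = 1 must return W.

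**Two readings.** Let d = 102.78 − 2.78R.

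- Literal: (W/d)/100
- Grouped: W/(d/100)

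**Values for W = 50 kg.**

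| R | d | Literal (kg) | Grouped (kg) | Grouped/W |
|---|---|---|---|---|
| 1 | 102.78 − 2.78 = 100.00 | 50/100.00/100 = 0.0050 | 50/1.0000 = 50.0 | 1.000 |
| 5 | 102.78 − 13.90 = 88.88 | 50/88.88/100 = 0.0056 | 50/0.8888 = 56.3 | 1.125 |
| 9 | 102.78 − 25.02 = 77.76 | 50/77.76/100 = 0.0064 | 50/0.7776 = 64.3 | 1.286 |

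Only the grouped reading returns W at R = 1.

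**Ratio of the readings.** Grouped/literal = (100W/d)/(W/(100d)) = 100 × 100 = 10,000. Both W and d cancel, so the ratio is the same for every participant, machine, visit and repetition count.

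**Effect on the planned analyses.** Multiplying an outcome by a constant c has these consequences:

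- ANOVA and ANCOVA: the between-group and residual mean squares are both multiplied by c², so F and p do not change. In ANCOVA, rescaling the baseline covariate by c only rescales its coefficient.
- MANOVA: the usual test statistics do not change when an outcome is rescaled.
- Standardized effects: the difference and the SD both scale by c, so their ratio does not change.
- Percent change: c cancels.
- Means, SDs, differences and unstandardized coefficients in kilograms: all scale by c.

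**Illustration of change.** Take 40 kg for 9 repetitions at baseline and 45 kg for 7 at follow-up. At R = 7, d = 102.78 − 19.46 = 83.32.

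- Grouped: 45/0.8332 − 40/0.7776 = 54.009 − 51.440 = 2.57 kg; 2.568/51.440 = 4.99%.
- Literal: 45/83.32/100 − 40/77.76/100 = 0.00026 kg, again 4.99%.

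**The case for a change.** The strongest case for a correction is that the protocol chose to print the formula, and the printed formula fails a check that any reader can make. This is therefore a misstatement and not a detail left to an analysis plan. The kilogram means and SDs, which section 3.4 says will be presented, are on the affected scale. The explicit slashes and brackets look like typed inline text, and a stacked fraction would not necessarily leave them behind. If different people scored different records under different readings, the factor would no longer cancel. The remedy is one pair of brackets.

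The arithmetic part of this stands: read literally, the string is wrong by 10,000. The rest carries little weight. The text was extracted by a program, and a stacked fraction could have produced the same string; the document at hand cannot settle this. The harm requires literal coding, and nothing in the protocol points to that. Mixed scoring would put values near 0.005 kg beside values near 50 kg in the same column, which is hard to miss. The regression consequence is also uncertain: section 3.4 does not say whether improvement is absolute or in percent, and percent change is immune.

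**Conclusion.** No change to the plan follows. If the original file prints the equation inline as shown, the slip is clerical: one pair of outer brackets is missing, and the intended form is 1RM = W/([102.78 − 2.78(R)]/100). If the original shows a stacked fraction, there is no slip at all.

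An analyst will reach the intended form without help. The protocol identifies the equation by name and reference and says what it estimates. Its constants give exactly 100 at one repetition, which has a purpose only if the division by 100 belongs to the denominator. Under that reading the multiplier runs from 1.000 at R = 1 to 1.286 at R = 9.

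The discrepancy is large on paper, a factor of 10,000, but it is constant. It cannot alter F, p, a standardized effect or a percent change, and on the kilogram scale it would show at once. This conclusion assumes that all records are scored with one reading and that someone looks at the strength values before they are reported. Both are ordinary practice, and the protocol gives no reason to doubt either.

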3.4 Data analysis

All statistical analysis will be performed using SPSS Statistical Software (IBM Corp. Released 2016. IBM SPSS Statistics for Windows, Version 24.0. Armonk, NY: IBM Corp). Difference in outcome measures between the groups will mainly be evaluated using analysis of variance (ANOVA), multivariate analysis of variance (MANOVA) and analysis of covariance (ANCOVA) The association between the exercise professional's level of education and knowledge base and participants adherence to exercise and/or improvement in health and physical fitness, will be assessed using linear regression, controlling for cofounding variables. Data will be presented as frequency, percentage or mean with standard deviation (SD). Transcripts from the in-dept interviews, will be analyzed using thematic analysis.

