3.1.1 Exercise professionals (n=25)

A total of 25 exercise professionals, working full time as a personal trainer will follow up the participants at one of the following fitness clubs: Feel24, PT-group, Nr1 Fitness, Trento or Spenst. These fitness clubs are located in the same area the participant lives and receives regular follow-up care from their GP. To minimize error caused by limited knowledge of the ABEL-app, and to ensure that the exercise professionals know how to use this system for

coaching participants and data collection, the exercise professionals have finished a webbased onboarding program, consisting of six modules, of 45 to 60 minutes. In the five first modules, the exercise professionals were educated in the functionality of the ABEL-app. The sixth module was led by two members from the ABEL-project group, where the exercise professionals learned how to conduct testing of participants and instructed in standardized test protocols. In addition, instruction videos for all test protocols will be uploaded on the ABEL-app.

To be included in the research project as an exercise professional, the qualifications and requirements are:

- A minimum of three years' experience working part-time as a personal trainer, and delivered ≥ 80 training sessions/per month, in three of the last five months, with one of the following qualifications:
 - 1) Higher education: bachelor/master in sports science, or other relevant health education (physiotherapy, nursing, osteopath, chiropractor).
 - 2) Practical experience: A personal training education (one-year education/60 credits), well as 2000 hours of delivered exercise sessions with clients.
- Completed an exam, developed by researchers at NSSS and Kristiania University College, that covers knowledge in: central elements of exercise (anatomy, physiology, biomechanics, aerobic endurance, and muscular strength), physical activity and health, coaching and motivation, source criticism and methodology, and exercise among patients with obesity. The test scores will be used to evaluate associations between the exercise professionals' level of competence and participants adherence to exercise and/or improvement in health and physical fitness. The project will therefore also obtain informed consent from the exercise professionals.
- Signed "professional ethics guideline" document.
- Completion of "Norway's Anti-Doping Agency's" and "Norway's counseling About Eating Disorders eLearning module.

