3.1.2 Random allocation

Each participant will be randomly assigned (1:1:1:1) to one intervention group, HIGH, MEDIUM, LOW or CONTROL following a simple computer-based randomization program. All participants included in the study will conduct the baseline assessments before the randomization procedure. The study design will not allow for further masking of study participants or the exercise professional (caregivers to the interventions). Those from the research group involved in inclusion of the participants or follow-up measurements will not have access to the group allocation list. Further, all measurements will be completed and plotted without the research group information of group allocation. The statistical analyses will be done in SPSS, following a predefined analysis plan and before unmasking the study arms.

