3.3 Outcome measures

Date will be collected at baseline, continually during, and immediately following the intervention period.

Monitoring adherence to subscribed exercise sessions:

Measures of adherence will be collected through the ABEL-app. Sessions performed with the exercise professional will be logged through the ABEL-app of the exercise professional, while sessions performed independently will be logged through the ABEL-app of the participant. Adherence will be measured by attendance (percentage of exercise sessions completed out of exercise sessions offered), as well as intensity (physical exertion of sessions) and duration (duration of sessions) (44).

Questionnaire (approximately 25 minutes to complete):

- **Background information:** Covering age, smoking, level of education, household income. In addition to information about physical activity behavior (fulfillment of physical activity recommendations, as well as weekly frequency, duration and modes of physical activity).
- **Health-related quality of life**: Will be measured by a Norwegian version of The MOS 36-item short-form health survey (SF-36) (45).
- **Self-efficacy**: Will be measured by a Norwegian abbreviated validated version of the Self-Efficacy Survey developed by Sallis et al. (46).
- **Perceived social support from family and friends**: Will be measured by a Norwegian version of a previous validated survey (47).
- **Stages of change:** Will be measured with a previously conducted questionnaire on exercise professionals' effect on changing attitudes towards physical activity according to upward moving in the stages of change model (48). To achieve high cross-language validation when translating the English version into Norwegian language, we used a forward-backward translation technique, involving three members of the research group. A bilingual acquaintance of the research group with English as mother tongue will finally assured the quality by comparing the "new" English version" with the original version.
- **Barriers to exercise:** Questions will be based on identified barriers in a previous study among Norwegian adult population (n= 12 504) (49) and among fitness club members (50). Eighteen barriers will be included in the questionary.
- **Motivation for exercise and physical activity:** Will be measured by a Norwegian version of the validated survey BREQ-2 (51).

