 Urinary incontinence: Will be measured using a Norwegian version of the Incontinence Questionnaire-Short Form (ICIQ-UI SF) (52). Awareness and knowledge about pelvis floor muscles exercises will be assessed by single questions: "Do you do pelvic floor muscle exercises?" If yes, how many times weekly?" "If yes, has your exercise professional provided you any coaching on pelvic floor muscle exercises?"

At follow-up, we will add questions regarding how satisfied participants are with the digital and physical follow-ups, as well as perceived social support from their exercise professional during the trial period.

Health factors:

- **Blood pressure, waist circumference and BMI:** Measures of blood pressure, waist circumference and BMI (height and weight) will be conducted during health screening at the GP. These variables are strongly associated with development of non-communicable diseases and can therefore be a low-cost indicator of general health which is minimally intrusive for the participant (53). Data will be scanned and sent to NSSS via password protected zip-files after the posttest, and stored on a secure data area.
- **Glycated hemoglobin and cholesterol:** Testing self test kits (Tigeni, Norway) will be given to all participant at baseline and follow-up for collection of blood sample markers: glycated hemoglobin and cholesterol (LDL, triglycerides and HDL). All values will be collected through capillary blood drawn from finger pricks. The participants will conduct the finger pricks test at their respected fitness club. The samples will be collected via DHL and sent to Tigeni for further analyses. Data will be collected by the GP and sent to NSSS via password protected zip-files after the posttest and stored on a secure data area. These testing kits have been shown to be reliable and valid for testing for markers as described above (54), and are considered to be practicable for the participants (55). Furthermore, due to the spread among the participants geographically, there is a need for achievable methods for collecting these markers.

Physical fitness:

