the purpose of this project, we will also add questions regarding how satisficed participants where with in-person and digital follow-up by their exercise professional.

• General practitioners (n=8): The GPs recruited in the project will participate in a semi-structured in-depth interview (approximately 45 min). The interview will be led by researchers from the project group, audiotaped and transcribed verbatim. Questions will be based on a previous qualitative study from 2006, conducted on GPs in Norway (29).

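### Aim 4 relates women's outcomes to traits of 25 exercise professionals with no term for the professional; run on participants, its intervals are too narrow whenever the within-professional correlation is positive

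*Protocol*

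**What the plan says.** Section 2.1 sets aim 4: "Is adherence to exercise and succeeding health effects associated with the exercise professionals' level of education and knowledge base". Section 3.1.1 supplies the explanatory variables and the number of professionals: "A total of 25 exercise professionals, working full time as a personal trainer will follow up the participants", and "The test scores will be used to evaluate associations between the exercise professionals' level of competence and participants adherence to exercise". Section 3.4 gives the method. The association "will be assessed using linear regression, controlling for cofounding variables".

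Section 3.1.2 sets the allocation: "Each participant will be randomly assigned (1:1:1:1) to one intervention group". Table 1 gives the control arm no coaching. The interview paragraph of section 3.3 speaks of "in-person and digital follow-up by their exercise professional", which supports one professional per woman.

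The protocol does not name the unit of analysis for aim 4. It mentions no random effect, multilevel model, cluster-robust error or aggregation by professional.

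**The concern.** Education and exam score are constant within a professional. With such a regressor, women who share a professional add less information than the same number of independent women, and a regression that treats them as independent understates the standard error.

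Adjusting for participant confounders does not remove the correlation. Fixed indicators for each professional are no remedy either, because they would be fully collinear with the trait under study.

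A positive correlation is plausible from the protocol itself:

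- **All outcomes.** Shared coaching is a route for every outcome. Aim 4 presupposes that professionals differ, and unless the two measured traits explain all of that difference, some correlation remains.
- **Adherence.** Professionals log the supervised sessions, but "sessions performed independently will be logged through the ABEL-app of the participant".
- **Fitness.** Exercise professionals run the fitness tests. The protocol does not say that the tester is the woman's own coach.
- **Other health measures.** "Measures of blood pressure, waist circumference and BMI (height and weight) will be conducted during health screening at the GP", and glycated hemoglobin and lipids are analysed by an outside laboratory. The ICC may be smaller for these.

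Section 4.2 plans one article per research question, so aim 4 would be published on its own. Intervals that are too narrow would report a chance link between qualifications and outcome too often.

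**Working it through.** The protocol gives no ICC, significance level or power figure for this aim, so there is no stated figure to reproduce. A two-sided 5% level and the ICC range are assumptions.

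**Inputs**

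- 200 women in four equal arms (3.1, 3.1.2), three of them coached: 200 × 3/4 = 150.
- 25 professionals (3.1.1): 150/25 = 6 coached women each.

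**Formulas**

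- Design effect for a regressor constant within professional, equal caseloads: D = 1 + (6 − 1) × ICC.
- The true standard error is √D times the one reported, so the interval has 1/√D of its proper width.
- True size of a nominal 5% test: 2 × (1 − Φ(1.96/√D)).
- Example at ICC 0.10: D = 1.50, √D = 1.225, 1.96/1.225 = 1.60, size 11.0%.

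**Equal caseloads**

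| ICC | D | √D | Interval too narrow by | True size | True coverage of a 95% interval |
|---|---|---|---|---|---|
| 0.01 | 1.05 | 1.025 | 2% | 5.6% | 94.4% |
| 0.02 | 1.10 | 1.049 | 5% | 6.2% | 93.8% |
| 0.05 | 1.25 | 1.118 | 11% | 8.0% | 92.0% |
| 0.10 | 1.50 | 1.225 | 18% | 11.0% | 89.0% |
| 0.20 | 2.00 | 1.414 | 29% | 16.6% | 83.4% |

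**Unequal caseloads.** An assumed set of 1 to 14 women per professional (150 in total, coefficient of variation 0.57) has Σm²/Σm = 7.95, so D = 1 + 6.95 × ICC. The true size is then 5.8%, 6.6%, 9.1%, 13.2% and 20.5% at the same five ICCs.

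**Degrees of freedom.** The critical value is 2.069 on 23 df (25 professionals) against 1.976 on 148 df (150 women), a ratio of 1.047. With arm terms in the model the participant-level df are 146, which makes no practical difference.

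**Simulation check.** 6,000 runs per setting, 150 women, 25 professionals, no true effect of the trait, arm as a fixed effect. The mixed model has a random intercept for professional and Satterthwaite df. E is equal caseloads and U the unequal set.

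| ICC | OLS size, E / U | Mixed-model size, E / U | Width, mixed over OLS, E / U |
|---|---|---|---|
| 0 | 4.9 / 5.2% | 4.0 / 4.0% | 1.07 / 1.08 |
| 0.01 | 6.0 / 6.0% | 4.2 / 4.0% | 1.09 / 1.11 |
| 0.02 | 6.5 / 6.7% | 4.6 / 4.5% | 1.11 / 1.13 |
| 0.05 | 8.2 / 9.2% | 5.1 / 4.8% | 1.17 / 1.20 |
| 0.10 | 11.0 / 13.3% | 5.3 / 5.3% | 1.27 / 1.32 |
| 0.20 | 17.1 / 20.4% | 5.0 / 5.1% | 1.47 / 1.53 |

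Participant-level regression (OLS) agrees with the formula, and the mixed model holds its level. Regressing one mean per professional on the trait also holds it (5.0% to 5.6%). Its intervals are 1.02 to 1.45 times the OLS width with equal caseloads and 1.28 to 1.60 times with unequal ones.

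**The case against.** The strongest objection is that section 3.4 is unspecific, not wrong. It states no unit, and a regression on 25 professional means is also a linear regression and would be valid. Section 3.1.2 refers to a predefined analysis plan that is not at hand and may deal with this. That is why the finding is conditional. It does not remove the finding, because the protocol names a method for this aim and describes the outcomes as the participants' own; read naturally, that method treats the women as independent.

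The size also rests on assumed ICCs and caseloads. That stands: the result runs from negligible at ICC 0.01 to 20.5% at ICC 0.20 with uneven caseloads, and the protocol cannot say where this trial lies.

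Loss to follow-up softens the figures a little. With an assumed 20% loss there are 4.8 women per professional. At ICC 0.10, D = 1 + 3.8 × 0.10 = 1.38 and the true size is 9.5%, just short of double.

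Professionals may also share a club, and the simulations include no correlation by location. That limits how far they vouch for the mixed model here, but it does not support leaving the nesting out.

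**Conclusion.** The concern holds, as a minor point. If aim 4 is analysed on participants and the within-professional correlation is positive, its intervals are too narrow and its tests reject too often. The effect is trivial at ICC 0.01 and material from about 0.05 (8.0% to 9.1% for a nominal 5% test). With all 150 coached women analysed, the error rate at least doubles from ICC 0.10 (11.0% to 13.2%).

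These figures rest on one professional per woman, about six coached women per professional, and ICCs that are assumed and may differ by outcome. Only the stated precision is affected, not the coefficient. Whether clustering by professional also matters for the arm comparisons is a separate question, not raised here. The weight is modest because aim 4 is a non-randomised association in a feasibility study.

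**What to change.** In section 3.4, for aim 4 only and in coached participants only (HIGH, MEDIUM, LOW), write:

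*The association will be assessed with a linear mixed model (SPSS MIXED) with a random intercept for exercise professional and fixed effects for arm, baseline value (where the outcome has one; adherence has none), exam score or education, and the listed confounders, with Satterthwaite degrees of freedom.*

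Section 3.4 names no confounders at present, so the list has to be added. Report the ICC for each outcome with its confidence interval, and state that precision is limited by there being 25 professionals.

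Regressing arm-adjusted means per professional on the trait is an acceptable alternative, though less precise when caseloads are unequal. If that is what is meant, say so. If the predefined analysis plan already handles the nesting, align section 3.4 with it.

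The change needs one sentence and the confounder list, the same software and no new measurements, but each coached woman's record must carry her professional's identifier. The price is wider intervals: with equal caseloads about 7% at ICC 0, 17% at 0.05 and 47% at 0.20; with the assumed unequal ones 8%, 20% and 53%. The test is slightly conservative when the ICC is near zero (about 4.0%).
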